## SUMMARY

Promotor	INRA
Main investigator	[name]
Co-Investigators	[name], [name], [name]
Title	Identification of new biomarkers of banana and tomato intake
Rational	In epidemiological studies, dietary intakes are assessed by questionnaires, an approach with inherent limitations associated with self-reporting : memory bias, difficulty to estimate portion size, insufficient coverage of the dietary diversity... The use of biomarkers of food intake should markedly improve the accuracy of dietary assessment, However, only few validated biomarkers are available. A large European project (FoodBALL) was funded by the JPI HDHL to identify a large range of new biomarkers of intakes, using untargeted metabolomics on urine and plasma samples collected in a series of controlled nutritional intervention studies.
Objective	The BioBanaTom study aims, in the framework of the FoodBALL project, at identifying new biomarkers of intake for banana and tomato, two important foods of the European diet.
Evaluation criteria	Main Criteria: Identification using metabolomics of plasma and urine metabolites specifically associated to banana and tomato intake, for validation as biomarkers. Secondary criteria : Obtention of reference metabolomics profiles which may be related to metabolic impact of an acute intake of tomato or banana.
Methodology	Cross-over randomized, open, controlled
Number of subjects	12
Undesirable effects	No undesirable effect expected beyond those link to blood sampling (small local hematoma, slight local inflammation)
Recruitment modalities	Volunteer file of UEN declared to the CNIL, mailing CHRU and INRA Clermont-Ferrand-Theix, local medias. The selection of the volunteers will be performed during medical inclusion visits.
Main selection criteria	Inclusion criteria Men and women, healthy (normal medical and biological exam), non-smoking, aged 18 to 40, BMI>18,5 and <30 kg/m  , with no aversion for banana or tomato. Exclusion criteria Smokers, diagnosed with infectious or chronic disease, under medication (except contraception pill), having followed an antibiotic treatment in the last 3 months, consuming dietary supplements several times a week, pregnant and lactating women, vegetarian as the protocol implies consumption of standardized meal containing meat.

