Protocol description	Written consent will be obtained after complete information of the subjects about the objectives, and the nature and possible risks of the study (informed consent form in duplicate, one copy given to the volunteer). The protocol will be explained in details, with objectives and constraints, according to the information form, by the scientist in charge. A clinical exam and a check-up of all selection criteria will be performed by the main investigator or another medical doctor.  At the inclusion visit, subjects will have a medical exam including questionnaire

	
regarding past medical history, family background, medical treatments and standard clinical exam (weight, height, blood pressure) and a blood sampling. A food frequency questionnaire will also be completed. The conformity to the selection criteria will be checked during this medical exam. The selected subjects will be definitely included after validation of the selection criteria by the investigator.
 
The volunteers will consume in 3 distinct experimental periods either a control drink (oral nutritional complement Fresubin, 250 mL), or 240g banana (and 150 ml Fresubin), or 300g tomato (with 12 g sunflower oil and 150 mL Fresubin). Every volunteer will consume the 3 test foods, in a randomized order. After test food intake, urine will be collected over 24h in 7 fractions. Blood samplings will be performed before the food consumption (t0) and in post-prandial period (4 samplings at 1h, 2h, 4h et 6h), as well as on the following day in fasting state (t24h). the volunteers will follow a tomato and banana-free diet during the study days, as well as a more restrictive diet, without plant-based food, on the sampling days and on the day before. A 24h recall will be filled for the dietary intakes on the day before the sampling days (D2).
 
Samples will be analyzed using an untargeted metabolomics approach (LC-MS, GC-MS et RMN) with the aim to identify new biomarkers of tomato and banana intake.
 
The total volume of sampled blood will be 154 ml per subject.

Duration	
Duration of the study for every volunteer : 8 weeks
 
Total duration of the study: 6 months for the subject selection and realization of all experimental periods for all the volunteers
 
Total duration of the project : 3 years

Indemnities	350€ per subject

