## 10 - BALANCE BENEFITS/RISKS

The risks involved in participating in this experiment are minimal. A venous puncture is comparable to a normal blood drawn and the only risk is that of a small local hematoma.

The inconveniences which can result of blood collection are possible infectious or inflammatory problems. These complications are exceptional and all the necessary measures of asepsis are taken to avoid them.

The food products that will be provided are commercially available products and for this reason do not bring any health risks.

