### **11-3 INSURANCE**

The sponsor, INRA has an insurance (N° 4623359604) which is in accordance with the legal requirements. This insurance provides cover for damage to research subjects through injury or death caused by the study product and/or study procedures.

It is to note that the non compliance with the legal requirements of the research (absence of CPP opinion, absence of ANSM's authorization, non consent of the person, the continuation of a suspended or speechless research) is an exclusion clause of the guarantee.

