#### -SUSPECTED UNEXPECTED SERIOUS ADVERSE REACTION (SUSAR)

A SUSAR is both:

- an SAE that is judged to be at least possibly related to the study product by the either investigator or sponsor, and
- unexpected (not listed in the Product Information Brochure)

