#### *11-6-2 (Serious) Adverse events handling*

#### -(S)AE RECORDING

Any (S)AE as reported spontaneously by the subject or observed by the investigator or staff, is recorded on the AE form during the course of the study. The investigator must ensure that all required information is captured on this form, including the nature, onset, duration, and severity of the event, the relationship to the study product, and the action taken.

Only untoward medical events occurring after first study product intake are recorded as (S)AE (Events occurring during the Baseline period and/or before first study product intake are recorded as pre-existing condition on the Relevant Medical History and Pre-Existing Conditions page in the CRF).

When a subject undergoes a medical intervention or hospitalisation in absence of an Adverse Event (such as treatment for a pre-existing condition or hospitalisation for elective surgery or diagnosis), this intervention/hospitalisation must be reported on the AE page and not as SAE. These procedures will be handled like AEs, and timelines for reporting are the same as for reporting AEs. Complications or prolongations of hospitalisation that result from such procedures must be reported as (S)AEs, according to the applicable reporting timelines and procedures.

The severity of any (S)AE is scored as follows:

- Mild: transient or mild discomfort; no medical intervention/therapy required
- Moderate: mild to moderate limitation in activity; some assistance may be needed; and/or minimal medical intervention/therapy required
- Severe: marked limitation in activity; some assistance usually required; and/or significant medical intervention/therapy/hospitalisation required

The relationship of the (S)AE to the study product is assessed as being not related / unlikely related / possibly related / probably related / definitely related.

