#### -SAE REVIEW AND REPORTING BY THE SPONSOR

In case the SAE is a potential SUSAR, the Medical Monitor must decide whether unblinding is required.

All SAEs are reported to the accredited Ethics Committee that approved the protocol. SAEs are reported annually as line listings or according to the requirements of the Ethics Committee, SUSARs

are reported within 7 days (fatal and life threatening events) or 15 days (other events).

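### Adverse events are judged for causality only against the study product, although the only harms the protocol expects come from blood sampling, so a serious procedure-related event has no stated Ethics Committee deadline

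*Protocol*

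**What the plan says.** **Expected harm.** The Summary states: "No undesirable effect expected beyond those link to blood sampling". Section 10 agrees: "The inconveniences which can result of blood collection are possible infectious or inflammatory problems". It calls such complications exceptional and says that the commercially available foods carry no health risk.

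**Causality.** Section 11-6-2, under (S)AE recording, lists among the items for the AE form "the relationship to the study product, and the action taken". The scale that follows begins "The relationship of the (S)AE to the study product is assessed as being not related" and runs up to definitely related. Neither place offers a category for study procedures.

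**SUSAR.** Section 11-6-1 sets two conditions. The first is "an SAE that is judged to be at least possibly related to the study product", as judged by either the investigator or the sponsor. The second is that the event is not listed in a product information brochure.

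**Reporting clocks (11-6-2).** The investigator sends the initial report of an SAE to the sponsor's delegate within 48 hours, with no causality condition. SUSARs go to the Ethics Committee within 7 or 15 days. For the rest, "SAEs are reported annually as line listings or according to the requirements of the Ethics Committee". The sponsor subsection also asks the Medical Monitor to decide on unblinding for a potential SUSAR.

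**Start of recording (11-6-2).** Only events after the first intake of study product count as (S)AEs. Earlier ones are entered as pre-existing conditions.

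**Duration.** The Summary gives: "Total duration of the study: 6 months for the subject selection and realization of all experimental periods for all the volunteers".

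**The concern.** The risk that the protocol names and the rule by which it judges risk do not meet. All expected harm is procedural, while relatedness is defined only in terms of banana, tomato or Fresubin. A site that follows the text has nowhere to record that a catheter caused an event, and the one route with a fixed Ethics Committee deadline is closed to that event. The point at which recording starts also leaves out the screening draw and the minutes around the first catheter insertion.

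What is at stake is prompt and correctly labelled information for the Committee on the main foreseeable risk to healthy volunteers. The endpoints and the metabolomic analysis are not touched.

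**Working it through.** The plan gives no figure to reproduce. The check follows one hypothetical event through the rules and then does the small arithmetic on timing and exposure.

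**A. A volunteer is hospitalised with a catheter-site infection that begins after first product intake.**

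1. Is it serious? Yes. Inpatient hospitalisation meets the SAE definition in 11-6-1.
2. Is it recorded? Yes, because onset is after first product intake. Nature, onset, duration, severity and action taken are all captured.
3. How is causality scored? The scale asks about the study product. The food or drink did not cause the infection, so the score is not related, or at most unlikely related.
4. Can it be a SUSAR? No. The first condition requires at least possible relation to the study product. The brochure test in the second condition is never reached.
5. Which clocks apply?

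| Route | Applies? | Deadline |
|---|---|---|
| Investigator to sponsor's delegate | Yes | 48 hours |
| SUSAR to Ethics Committee | No | 7 or 15 days |
| SAE listing to Ethics Committee | Yes | Annual, or as the Committee requires |
| Sponsor's duty to report increased burden or risk (11-6-3) | Possibly | None stated |

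**B. Timing of the annual listing.** The interval is 12 months and the conduct phase is 6 months, so 12 / 6 = 2. The documents do not say when the annual clock starts. If it starts with the study, an event in month m (0 to 6) waits 12 − m months, that is 6 to 12 months, and the first listing comes 12 − 6 = 6 months after conduct ends. If the clock runs from some other date, the listing may fall within the conduct phase, and the wait may be anything from 0 to 12 months.

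**C. Exposure.** Inputs are the screening blood sample, one catheter per intervention day (removed after the 6 h sample) and one 24 h sample per period (section 6-1), with 3 periods and 12 volunteers. Assume one puncture per catheter and per single draw.

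- Catheter placements: 12 × 3 = 36.
- Punctures per volunteer: 1 + 3 + 3 = 7. Total: 7 × 12 = 84.
- Punctures before first product intake: 1 screening draw + 1 first catheter = 2 per volunteer, so 2 × 12 = 24.
- Punctures after first intake: 84 − 24 = 60.

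Section 6-1 places the catheter before the test food is eaten, so the first insertion falls in the unrecorded window. What matters is when the event occurs. A complication of the first catheter that appears after intake is still recorded as an (S)AE, whereas one that appears at insertion, or after the screening draw but before intake, is not.

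These are counts of opportunities, not of events. The documents give no complication rate.

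**The case against.** The strongest reply is that a serious catheter event would not be lost. The sponsor's delegate receives it within 48 hours whatever its cause, and section 5-4 also requires immediate notice to the sponsor where a subject is withdrawn for a serious event. Section 11-6-3 obliges the sponsor to tell the Committee of any occurrence that could worsen the burden or risk to participants, with suspension possible. The annual listing is only one of two alternatives, and the Committee's own requirements, like the national rules that sections 11-2 and 11-4 invoke, are not in these documents. All of this stands and limits the point. What remains is that no deadline to the Committee is stated for such an event.

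Several stronger readings are tempting and should be resisted:

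- **That such an event escapes expedited reporting altogether, or is certain to reach the Committee only once a year.** The 48-hour report, the second half of the listing sentence and section 11-6-3 rule this out.
- **That the trial would report no related events by construction.** A reaction to a food could still be scored as related, and neither protocol section 9 nor the SAP plans a safety table.
- **That the insurance section contradicts the safety section.** Section 11-3 covers harm "caused by the study product and/or study procedures". That shows the sponsor had procedural harm in view, but insurance cover and safety reporting may differ in scope.
- **That judging expectedness against the risks in the Summary and section 10 would be a sufficient repair.** Infection and inflammation are listed there, so a catheter infection would count as expected and still not be a SUSAR.

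It is also fair that few events can be expected in 12 healthy volunteers and that a catheter event would be recognisable from its description on the form.

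**Conclusion.** The concern holds in limited form. As written, a serious procedure-related event is scored not or unlikely related, cannot be a SUSAR and has no stated Ethics Committee deadline. By default it may surface only in an annual listing, which can fall after the 6-month conduct phase. Separately, complications that occur before first product intake are not recorded as (S)AEs. On the one-puncture assumption, that window contains 24 of 84 planned punctures.

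The conclusion assumes that the site applies the causality wording literally and that the Committee has set no faster requirement. If it has, the timing gap closes, but the misplaced causality reference and the recording start remain. This is a gap in safety reporting that is worth closing because closing it is nearly free. It does not threaten the study's scientific conclusions.

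**What to change.** 1. In 11-6-2, rate each (S)AE twice: relationship to the study product and relationship to a study procedure.
2. In 11-6-2, start (S)AE recording at the first study procedure instead of at first product intake, so that the screening draw and first catheter placement are covered.
3. In the sponsor-reporting part of 11-6-2, replace the annual default with forwarding to the Ethics Committee, within a stated short interval after the sponsor's receipt, of every SAE at least possibly related to the product or to a procedure, whether or not it is expected. This works without relying on the SUSAR definition, whose relatedness and expectedness tests are both tied to the product.
4. Delete the unblinding step, since the Summary describes the study as open and section 4 says blinding is not possible.

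The cost is one more item on the AE form and a few sentences of protocol wording. With few events expected in 12 healthy volunteers, the added reporting work is negligible. No change to the statistical analysis is needed.

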#### -SAE REPORTING BY THE INVESTIGATOR

The investigator must completed SAE report. The initial report must be sent to the delegated person by the sponsor within 48 hours (2 working days) after first notice, the follow-up report as soon as relevant new information is available.

#### -SAE REVIEW AND REPORTING BY THE SPONSOR

In case the SAE is a potential SUSAR, the Medical Monitor must decide whether unblinding is required.

All SAEs are reported to the accredited Ethics Committee that approved the protocol. SAEs are reported annually as line listings or according to the requirements of the Ethics Committee, SUSARs

are reported within 7 days (fatal and life threatening events) or 15 days (other events).

#### -FOLLOW UP OF (S)AES

(S)AEs are followed-up by the investigator until they have abated, or until a stable situation has been reached. Depending on the event, follow-up may require additional tests or medical procedures as indicated, and/or referral to the general practitioner, a medical specialist, or another health care provider.

#### *11-6-3 New relevant and safety information*

The Sponsor will inform the investigator and the reviewing accredited Ethics Committee if anything occurs that may negatively affect the burden or risks of participation as foreseen in the research proposal. The study may be suspended pending further review by the accredited Ethics Committee, provided that suspension does not jeopardise the subjects' health. The investigator will take care that all subjects are kept informed.

#### **11-7 DATE HANDLING**

CRFs are records of data on each subject as defined by the study protocol. Entries on CRFs shall be made complete, legible and correct using a ball-point pen. Any mistakes shall be corrected by drawing a line over the old entry and by initialling and dating next to the correction. The investigator should file all data per subject. An explanation for the omission of any required data should appear on the appropriate CRF page or other data collection forms.

The last page of each visit shall be signed and dated by the investigator to indicate the overall responsibility.

Original completed CRFs will be collected by the sponsor for data entry and further data management and statistical applications. A copy of each CRF will be archived by the investigator. At each visit the clinical monitor will review all completed CRFs (since last visit) for completeness including signature, and will compare selected data with the subject's records.

In accordance with GCP and with the national data protection laws, all information concerning the subjects in the study must be treated as strictly confidential by all persons involved in the study including the clinical, medical and statistical monitor.

Such consent shall be deemed to have been given for disclosure to any person for whom the investigator is responsible at his centre, but only so far as required for the purposes of the study, and, in the case of disclosures to staff, only if such staff are bound by obligations of confidentiality no less strict than those set out herein.

The Commission Nationale de l'Informatique et des Libertés (CNIL) is responsible for ensuring that information technology remains at the service of citizens, and does not jeopardize human identity or breach human rights, privacy or individual or public liberties. The Commission fulfils its duties in pursuance of the law of January 6, 1978 as amended on August 6, 2004.

In accordance with this law, healthy volunteers are informed that their data are processed in an automated way and that they can access this file directly through the investigator or through the physician of their choice.

INRA, sponsor of the study, signed a commitment to comply with the "Reference Method" of the CNIL for the processing of personal data carried out in biomedical research (MR-001) conducted by INRA. The investigative team of the project (UEN-CRNH) is committed to the methodology of reference MR001.

### **11-8 REGISTRATION ON THE NATIONAL REGISTER OF VOLUNTEERS**

The healthy volunteers will be recorded on the national database of volunteers who participate to clinical researches, VRB (Volunteers for Biomedical Research) in accordance with the French regulations.

### **11-9 AMENDMENTS TO THE PROTOCOL**

There will be no alterations or changes to the protocol without agreement of all investigators and sponsor.

If such an agreement, the planned changes will constitute an amendment that will be attached to the protocol.

Any amendment must be notified to the ethic committee if the planned changes affect the ethical or medical-scientific study (evaluation criteria, addition of a new center ....). Minor modifications do not require a review of the ethic committee.

### **11-10 MONITORING**

The investigator must permit study-related monitoring visits, audits, review by the Ethics Committee and regulatory inspections, and allow direct access to source data and source documents provided that subject confidentiality is protected.

Monitoring includes on-site visits to assure that the investigation is conducted according to the protocol and in order to comply with applicable regulations and deadlines. On-site review of Case Report Forms (CRFs) includes the review of forms for completeness, clarity, and consistency with source documents available for each subject.

### **11-11 BIOLOGICAL COLLECTION**

The collection of biological samples described in this protocol (blood and urine samples) is reported to the competent authority (Article L1123-12). It can be stored at the end of the research for the study of certain biological parameters of interest in the same purpose (metabolomic analysis) initially planned in the protocol. All collected samples will be stored during 15 years after the end of the clinical study.

As mentioned in the protocol and subject information sheet, the collected biological samples can be stored at the end of the research, without change of purpose.

In case of a change of purpose, the Ministry of Research, the CPP and the Regional Hospitalization (if the facility is a health organization) are notified. Moreover, subjects will receive a new information which will permit them to express their opposition if they desire.

At the end of the study, urinary and blood samples collected will be stored at the Human Nutrition Unit, INRA Centre of Theix.

